## **Eligibility**

### **Inclusion Criteria:**

- Patients  $\geq 18$  years of age, both sexes - Diagnosis of MS for no more than 10 years - Residence in the Italian Region of Emilia Romagna, Italy

### **Exclusion Criteria:**

-EDSS (Expanded Disability Status Scale) < or  $=7$  -Diagnosis of Celiac Disease, Inflammatory Bowel Disease (Ulcerative Colitis or Crohn's Disease) -Evidence of Diverticular Colon Disease -Previous or ongoing neoplastic diseases of the digestive system -Endocrine disorders such as uncompensated hypothyroidism, diabetes mellitus in treatment, hypoparathyroidism, pheochromocytoma -Other neurological disorders such as M. of Parkinson's, S. of Shy Drager. -Taking drugs that affect intestinal transit (opiates, antiepileptic drugs, major antidepressants, calcium antagonists, anticholinergics, antidopaminergics)-Evidence of rectal or occult bleeding in the last 3 months -Infectious episodes in progress (\*)

NOTES: (\*) Rational: it is not considered ethical or functional to carry out such research in patients with infectious organ diseases requiring antibiotic and/or inflammatory therapies.

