**Study Protocol**

MS (Multiple Sclerosis) is the most common neurological disease involving disabilities in young adults, with Central Nervous System involvement in both the brain and spinal cord. In a recent review, its incidence in the United Kingdom is estimated at 7 new cases per 100,00 inhabitants per year, with a prevalence of about 100,000 patients. Bowel symptoms, in particular constipation and faecal incontinence, affect more than two thirds of MS patients, and have a significant impact on patients' quality of life (QoL) by significantly limiting their social, occupational and emotional life.

Recently, bowel management based on Transanal Irrigation (TAI) has also been proposed in patients with MS, but TAI efficacy on intestinal transit time and patient's compliance with TAI have not been defined yet.

The primary objective of the study is to assess the prevalence, characteristics, severity and impact on the Quality of Life of intestinal disorders in patients who consecutively refer to the neurological clinic for the diagnosis and treatment of Multiple Sclerosis at Ferrara University Hospital, Italy.

Secondary objectives are to correlate the severity and characteristics of constipation and fecal incontinence with intestinal transit time and the type of faeces evacuated according to the Bristol Stool Form Scale; to evaluate the costs in terms of the precautions (diapers, traverses, drugs, medicated clysm, etc.) and the time dedicated to the evacuation, and how these items change in relation to the use of TAI; and finally, to study the composition of the intestinal microbiota in MS patients in relation to the type of bowel characteristics, comparing it with the profile of the healthy population of the same region of origin, Emilia-Romagna, Italy.

The study proposed is a monocentric prospective observational study. The study population will be composed of patients who will consecutively refer to the Neurological Clinics of the University Hospital of Ferrara, Italy for a number of about 150 patients.

The study will consist of two phases. The first phase will be the selection of eligible patients by administering two self-filling questionnaires: PacQol (Patient Assessment of Constipation Quality of Life) and NBD (Neurogenic Bowel Dysfunction Score).

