## **Group Cohort**

This group will be composed by 150 MS patients who, consecutively, from the start of the study, will refer to the MS clinic of the Neurology Unit of the Ferrara University Hospital, Italy. The first 50 patients with a PACQoL score  $\geq 32$  will be asked to be willing to enter the next phase of the study that continues at the Coloproctological Outpatient Clinic of Ferrara University Hospital, Italy with an appointment provided by the neurologist with a pre-established schedule (with written consent).

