## **Intervention**

Patients with severe intestinal dysfunction impairment (PAC QoL score  $\geq 32$ ) will be offered the adoption of the TAI (Transanal Irrigation) with Peristeen Device as a way to manage their own evacuation, replacing any other measure used until that moment (suppositoires, enemas) with the exception of the possible intake of macrogols and/or prebiotics and/or probiotics which instead patients can continue. This treatment will be proposed to all patients with severe impairment of intestinal function.

The TAI training with Peristeen will be carried out at the surgical clinic of the Surgical Department of the Ferrara University Hospital, Italy, by the health personnel involved in the study, usually in a single session, but more sessions may be necessary, documented in CRF as VISIT 3, VISIT 3 bis and so on, until the end either with the continuation of the TAI independently for 4 weeks or with patient's exclusion from the study if the guarantees of appropriate use of the device will not be reached.

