## **Primary Outcome Measure:**

Outcome 1) Incidence and prevalence of intestinal dysfunction in Multiple sclerosis. Calculation of % of patients with a PACQoL score  $\geq 32$  for items B.1 to B.6 and/or a score  $\leq 11$  for item B.7 of the questionnaire.

Outcome 2) Characteristics of intestinal dysfunction in MS. Calculation of Agachan-Wexner scores, the Cleveland Clinic Index, the Altomare Questionnaire, and the NBD Score on the patient population that report a significant impact on their QoL of problems related to their bowel management and bowel disorders in general (Score  $\geq 32$  to PAC-QoL).

Outcome 3) Intestinal transit time in SM patients with intestinal dysfunction. Calculation of % of patients with a slowed Intestinal Transit Time ( $\geq 60$  hours for women and 55 hours for men)

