## **Study population**

The study population will be composed by 150 MS patients who will consecutively refer to the MS Outpatient Neurology Clinic at Ferrara University Hospital, Italy. The PAC-QoL questionnaire will be given to every patient. This questionnaire is a self-filled instrument validated and used in various studies to document the consequences that intestinal disorders and defecation have on everyday life. The first 50 patients with a PACQoL score  $\geq 32$  will be asked to be willing to enter the next phase of the study that continues at the Coloproctological Outpatient Clinic of Ferrara University Hospital, Italy with an appointment provided by the neurologist with a pre-established schedule (with written consent).

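### Followed as written, the EDSS exclusion admits only patients above 7, which does not fit a prevalence study in consecutive MS clinic patients; its direction, boundary and scope need confirming

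*Combined protocol and SAP*

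**What the plan says.** The Exclusion Criteria section opens with "EDSS (Expanded Disability Status Scale) < or", followed by an equals sign and the number 7. This is the only reference to EDSS in the document.

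The population is described in three other places:

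- Study Protocol: the primary objective is set in "patients who consecutively refer to the neurological clinic for the diagnosis and treatment of Multiple Sclerosis at Ferrara University Hospital".
- Group Cohort: "This group will be composed by 150 MS patients who, consecutively, from the start of the study, will refer to the MS clinic".
- Study population: "The study population will be composed by 150 MS patients who will consecutively refer to the MS Outpatient Neurology Clinic".

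Under Primary Outcome Measure, Outcome 1 is headed "Incidence and prevalence of intestinal dysfunction in Multiple sclerosis". Outcome 2 covers symptom scores in patients whose PAC-QoL score shows a significant impact. Outcome 3 is described as "Calculation of % of patients with a slowed Intestinal Transit Time".

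Two further details bear on the point less directly. Phase 1 uses "two self-filling questionnaires" (Study Protocol), and the Intervention section expects training to end in "continuation of the TAI independently for 4 weeks" or in exclusion from the study.

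**The concern.** An eligibility rule decides who is studied, and this one, applied as printed, removes every patient at or below 7. Nothing in the objectives, outcomes or rationale says that the study is meant for patients above 7. Staff screening from this text have no other passage to check the line against.

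What is at stake depends on where the rule applies, which the document does not say.

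- **Phase 1 (the 150 surveyed patients).** The denominator of Outcome 1 would consist only of patients above EDSS 7. The prevalence estimate would then describe a different population from the one named in the objective.
- **Phase 2 only.** Outcome 1 is unaffected. The restriction would fall on transit time (Outcome 3), on the scores in Outcome 2 that are collected at the surgical clinic, on the before-and-after TAI comparison and on the microbiota analysis.

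In both cases at least one primary outcome is touched. The Statistical analysis section contains nothing that could recover the intended population once a different one has been recruited.

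**Working it through.** The plan gives no figure to reproduce: neither the 150 nor the 50 for phase 2 has a stated derivation, and no EDSS distribution is given. The check is a logical one, followed by an illustration of size.

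**Step 1. What each reading admits**

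| Reading | Excluded | Admitted | EDSS exactly 7 |
|---|---|---|---|
| Literal text | EDSS ≤ 7 | EDSS > 7 | out |
| Sign reversed | EDSS ≥ 7 | EDSS < 7 | out |
| Inclusion limit in the wrong list | EDSS > 7 | EDSS ≤ 7 | in |

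The two candidate corrections disagree at exactly 7, so reversing the sign without checking the source could leave an error behind.

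**Step 2. Literal reading against the rest of the plan**

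- The Study Protocol section and Outcome 1 define the target as prevalence in consecutive clinic patients with MS. Neither carries a disability restriction.
- No objective, secondary outcome or rationale refers to EDSS above 7.
- Self-completed questionnaires and independent home use of TAI suggest, but do not show, that the cohort was not meant to consist only of patients above 7.

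**Step 3. Illustration of size**

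Input from the documents: N = 150 (Group Cohort; Study population). Assumed input: f, the share of clinic attendees with EDSS above 7.

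If 150 is the number enrolled, patients to assess = 150 / f, before any other exclusion. If 150 is the number screened, patients qualifying = 150 × f.

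| Assumed f | 150 / f | 150 × f |
|---|---|---|
| 5% | 150 / 0.05 = 3000 | 150 × 0.05 = 7.5, about 8 |
| 10% | 150 / 0.10 = 1500 | 150 × 0.10 = 15 |
| 20% | 150 / 0.20 = 750 | 150 × 0.20 = 30 |
| 50% | 150 / 0.50 = 300 | 150 × 0.50 = 75 |

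Both columns are shown because the population descriptions can be read either way. The point does not depend on any one value of f.

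**The case against.** The strongest reply is that the population descriptions prove little. Any eligibility rule narrows a consecutive series, and these sections are equally silent on the limit on time since diagnosis, coeliac disease, treated diabetes and transit-altering drugs. Their silence on EDSS is therefore not specific to EDSS. The missing rationale is also weak evidence, since only the infection exclusion is given one. This stands: the silence is supporting evidence only, and a reader who infers a strict contradiction between the sections goes further than the text allows.

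The indirect signs are thin too. A self-completed questionnaire is a type of instrument, and independent use of TAI may mean at home without clinic staff, not necessarily without a carer. Neither passage mentions disability. This also stands.

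A reader might go on to infer that the sign is certainly reversed. The documents do not support that. A misplaced inclusion limit explains the line equally well, and the literal text could be intended. The document does not define the scale beyond its name, so the argument here does not rest on what a score of 7 means clinically.

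An error in reading the PDF is possible. It is unlikely, because the comparison is partly in words before the equals sign and the 7, but it is not ruled out. Checking the source protocol settles it.

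Finally, the effect on prevalence is conditional on scope. That is true, but it does not remove the problem: the alternative scope moves the effect to Outcome 3 and part of Outcome 2.

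**Conclusion.** The point holds in this form: the criterion as printed admits only patients above EDSS 7, and a study run on it would not answer the stated prevalence question, or would run phase 2 in a restricted group that no objective asks for. It should be resolved before the plan is relied on.

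That the line is a mistake is likely, not proven, and the documents do not establish the intended direction or the handling of exactly 7. Nor do they support a claim that the prevalence outcome is necessarily affected, because the criteria might govern phase 2 alone.

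The size is illustrative only. At assumed shares of 5% to 50% above EDSS 7, enrolling 150 would take about 3000 down to 300 assessed patients; if 150 are screened, about 8 up to 75 would qualify. A reader might take these figures as showing that recruitment within the planned 2 years is infeasible. Without an EDSS distribution or a clinic attendance figure, that cannot be concluded.

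**What to change.** The investigator should:

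1. Check the EDSS line in the Exclusion Criteria against the source protocol.
2. Correct its direction or its placement between the two lists, as the source shows, and state explicitly how a score of exactly 7 is handled.
3. Add one sentence saying whether the Inclusion and Exclusion Criteria as a whole apply to the 150 surveyed patients or only to phase 2. The uncertainty concerns every criterion, so a sentence about EDSS alone would not be enough.
4. If the literal text is intended, restate the population and the objective in the Study Protocol, Group Cohort and Study population sections as limited to EDSS above 7.

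The sections must be reconciled by the investigator; no threshold is proposed here. The cost is one corrected line and one added sentence, with no extra patients or procedures. If the literal rule stands, the cost is instead a rewording of the population and objective, plus the sentence on scope.

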## **Study population**

The study population will be composed by 150 MS patients who will consecutively refer to the MS Outpatient Neurology Clinic at Ferrara University Hospital, Italy. The PAC-QoL questionnaire will be given to every patient. This questionnaire is a self-filled instrument validated and used in various studies to document the consequences that intestinal disorders and defecation have on everyday life. The first 50 patients with a PACQoL score  $\geq 32$  will be asked to be willing to enter the next phase of the study that continues at the Coloproctological Outpatient Clinic of Ferrara University Hospital, Italy with an appointment provided by the neurologist with a pre-established schedule (with written consent).

## **Statistical analysis**

Data will be expressed as median (interquartile range – IQR 25-75) and mean  $\pm$  standard deviation according to distribution assessed by Shapiro-Wilk test. Categorical data will be presented as numbers. Data will be analysed using Chi-square, t-student, and Mann-Whitney tests as appropriate. Cox regression analysis will be employed to assess independent predictors of improvement of intestinal dysfunction after Transanal Irrigation (TAI). Significance will be considered for values of  $p < 0.05$ . Statistical analysis will be performed with IBM SPSS Statistics for Windows, Version 24.0 (IBM Corp. Armonk, NY: IBM Corp.). The report will comply with the strengthening the reporting of cohort studies.

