## **Secondary Outcome Measures**

- 1) Correlation between Intestinal Transit Time and constipation scores in MS patients with intestinal dysfunction. To calculate the Correlation Coefficient between Intestinal Transit Time and the Bristol Score, the Agachan-Wexner Score, the Cleveland Clinic Index, and the NBD Score.
- 2) Correlation between Diet and intestinal dysfunction in MS patients. To correlate the Intestinal Transit Time and the Bristol Scale Score to the type of diet usually followed by patients in terms of adequacy of caloric intake compared to BMI, composition of macronutrients, and dietary fibre intake.
- 3) Efficacy of TAI in MS patients with intestinal dysfunction. Compare the Scores of the assessment scales used before and after the 4-week TAI treatment period, in order to detect a reduction in severity and an improvement in QoL score. Calculate a possible advantage or non-benefit of the costs of treatment with TAI compared to the previous bowel management.
- 4) Analysis of Microbiota in MS patients with intestinal dysfunction, before and after treatment with TAI. Compare the composition of the intestinal microbiota of MS patients with the known "healthy"

profile of the Italian population of North East of Italy and assess any changes after the period of treatment with TAI.

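### The rule for skewed data makes no exception for costs, so the cost effect of TAI would be reported on medians, and probably a rank test, rather than on mean cost per patient

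*Combined protocol and SAP*

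**What the plan says.** Three statements in the Statistical analysis section bear on this point.

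- Presentation: "Data will be expressed as median (interquartile range – IQR 25-75) and mean" ± SD, the choice being made "according to distribution assessed by Shapiro-Wilk test".
- Tests, in a separate sentence: "Data will be analysed using Chi-square, t-student, and Mann-Whitney tests as appropriate".
- A general significance threshold of p < 0.05.

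None of the three is limited to particular outcomes, and costs are not mentioned.

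Costs appear in two other places. The secondary objectives in the Study Protocol section include "to evaluate the costs in terms of the precautions (diapers, traverses, drugs, medicated clysm, etc" and similar items, and how these change with TAI. Secondary Outcome Measures, item 3, says: "Calculate a possible advantage or non-benefit of the costs of treatment with TAI compared to the previous bowel management". The sentence before it in the same item sets up a before-and-after comparison in the same patients for the scales: "Compare the Scores of the assessment scales used before and after the 4-week TAI treatment period". Neither place names a summary measure, a test or an interval for costs.

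**The concern.** Whether TAI saves money is decided by what is spent in total, that is, by the arithmetic mean cost per patient multiplied by the number of patients. A median cannot be scaled up in that way.

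Diary-based costs are counts of consumables multiplied by prices. They are usually right-skewed, with a few heavy users, so a Shapiro-Wilk test would usually reject normality. The plan then gives the median (IQR). On the usual reading of its test sentence, Mann-Whitney follows, because distribution is the only criterion the section mentions.

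Mann-Whitney asks whether a cost on TAI is as likely to lie above as below a cost before TAI. The signed-rank test asks whether the within-patient differences are symmetric about zero. Neither is the same as equal mean cost once the shape of the distribution changes between periods. Such a change is plausible: under the Intervention section, TAI replaces suppositories and enemas, so a varied mix of consumables may give way to one device routine. The typical patient could then pay more while savings among the few heavy users drop out of the result. If TAI made costs more variable, the error would run the other way.

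**Working it through.** **Inputs from the documents.** At most 50 patients are asked to enter the second phase (Study population). The number who complete TAI is not given, so 20, 30 and 50 are used. The threshold is 0.05, taken as two-sided. The same patients are measured before and on TAI. The plan has no cost figure to reproduce.

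**Assumed inputs.** Costs are lognormal with a true mean of 100 in both periods. The spread and the within-patient correlation (0, 0.3 or 0.5) are varied.

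**Why a rank test can reject at equal means.** For a lognormal cost with mean 100, the median is 100/√(1 + CV²).

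- Before TAI, CV 1.0: 100/√2 = 71.
- On TAI, CV 0.5: 100/√1.25 = 89.
- On TAI, CV 0.2: 100/√1.04 = 98.

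The log-scale variance is ln(1 + CV²): 0.693 for CV 1.0, 0.223 for CV 0.5 and 0.039 for CV 0.2. With independent costs, the probability that a TAI cost exceeds a cost before TAI is Φ(log ratio of medians / √(sum of log variances)).

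- CV 1.0 then 0.2: Φ(0.327/√0.732) = Φ(0.382) = 0.65.
- CV 1.0 then 0.5: Φ(0.235/√0.916) = Φ(0.246) = 0.60.

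Mann-Whitney takes 0.50 as its null value, so it tends to report TAI as dearer although mean cost is unchanged.

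**Rejection rates at equal means, CV 1.0 before and 0.2 to 0.5 on TAI, n = 20 to 50.** Mann-Whitney rejects in about 15-73%, almost always towards TAI being dearer. Signed-rank rejects in about 10-36% and the paired t-test in about 6-12%. At n = 50 the figures are about 73%, 34% and 10% for CV 1.0 then 0.2, and about 40%, 18% and 6% for CV 1.0 then 0.5.

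**A second grid, set by log-SD** (n = 50, correlation 0.3, equal means, 4,000 runs each):

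| Log-SD before / on TAI | Mann-Whitney | Signed-rank | Paired t |
|---|---|---|---|
| 1.0 / 1.0 | 2.5% | 5.0% | 4.1% |
| 1.0 / 0.7 | 28.0% (dearer) | 18.4% | 6.3% |
| 1.0 / 0.5 | 62.7% (dearer) | 34.4% | 8.2% |
| 1.2 / 0.3 | 95.4% (dearer) | 63.3% | 13.1% |
| 0.5 / 1.0 | 63.1% (cheaper) | 33.0% | 8.1% |

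Shapiro-Wilk flagged non-normality in at least one period in 96-100% of runs across this grid (n = 20 to 50). With the same shape in both periods, Mann-Whitney rejected in 0.7-5.3% over all sample sizes and correlations.

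**Converse case.** With log-SDs 1.0 and 0.5 and equal medians, the TAI mean is exp(−(1.0² − 0.5²)/2) = exp(−0.375) = 0.69 of the previous mean, a true saving of 31%. At n = 50 and correlation 0.3, Mann-Whitney rejects in 3% of runs and the paired t-test in 42%.

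**The case against.** **The plan does not state the rule in full.** The Shapiro-Wilk phrase belongs to the sentence on how data are expressed. Tests come in a separate sentence that also lists Student's t, and nothing says that Shapiro-Wilk selects among them. A reader might infer that the plan compels a rank test for costs, but the text does not support that. What stands without inference is the presentation half: skewed costs would be shown as medians.

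**No cost hypothesis is stated.** Item 3 says to compare the scales but to calculate the costs, which could mean plain costing with no p-value. A reader might infer that the trial will declare TAI significantly dearer or cheaper. That requires applying the general test sentence to costs, which is reasonable because the sentence covers data without exception, but it is not written.

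**Skewness alone does no harm.** The error needs a change of shape, and the documents give no prices or usage data to show one. Macrogols, prebiotics and probiotics may continue, and diaper use may too, so a CV of 0.2 on TAI is at the favourable end for this concern. In a mild case (CV 0.6 then 0.5, uncorrelated periods) rejection is 5-7%.

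**The most striking result is fragile.** With TAI truly 20% cheaper, Mann-Whitney calls it dearer in about 57% of runs at CV 1.5 then 0.2 and n = 50. This falls to 13% at CV 1.0 then 0.2, and to 3% at CV 1.0 then 0.5. A sample of 50 also assumes that everyone asked accepts and completes TAI.

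**Part of the error is a pairing fault.** Mann-Whitney is a test for independent samples and these data are paired. That is a separate flaw, and moving to signed-rank roughly halves the rates at n = 50. It does not remove the problem.

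**Conclusion.** The point holds in a limited form. The plan's only stated route for skewed data is the median, with Mann-Whitney as the one rank test named, and costs are not exempt. Neither answers whether mean cost changes with TAI. Whether a false conclusion would follow depends on three things the documents leave open: that costs are tested, that a rank test is chosen, and that TAI changes the shape of the cost distribution. The sizes shown depend on assumed lognormal costs and illustrate the mechanism; they do not forecast this study's error rate. If the shape is unchanged, the rank tests show no inflation. This is one part of one secondary outcome in an uncontrolled observational study, so the change is worth making but is not critical.

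**What to change.** Add to the Statistical analysis section: *Costs are exempt from the Shapiro-Wilk rule. Costs before and during TAI will be summarised as arithmetic mean (SD) per patient-week, with medians (IQR) as additional description. The cost result will be the mean within-patient difference with a 95% confidence interval from the paired t method. A bootstrap interval resampling patients will be given as a sensitivity check. Rank tests will not decide the cost conclusion.*

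The paired t interval is the better main analysis here. In simulation a bias-corrected bootstrap interval wrongly excluded zero in about 6-16% of runs. With equal shapes in both periods it did so in about 8-11%, where the paired t-test held about 3-6%.

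The cost is a few sentences of text and one extra run on data already planned. The downside is that the interval will be wide, can be moved by a few heavy users, and may cover somewhat less than 95% under strong skew with 50 patients or fewer. The report should say so.

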Patients with PacQol score  $\geq 32$  will be sent to the surgical clinic for the second phase. During the latter phase, patients will undergo a number of visits varying from 1 to 4 depending on the patient's willingness to continue the study. After the illustration of the purpose and protocol of the study to the patient,

classification of constipation and/or faecal incontinence in accordance with the Rome III Diagnostic Criteria will be assessed, with consideration of other possible etiopathogenetic factors other than MS. Further questionnaires will be filled in to evaluate the disease status (Constipation scoring system by Agachan-Wexner, Obstructed defecation score by Altomare et al, Fecal Incontinent grading scale by Jorge-Wexner); if the patient will consent to the continuation of the study, he will be given 7-days food diaries, evacuation diaries, radiopaque markers, stool collection container and appointment date for plain abdominal X-ray which may coincide with the appointment for examination number 2 (visit 2 or 3).

In particular, radiopaque markers Intestinal Transit Study will be performed according to the Bouchoucha procedure revised by Abrahamsson, which involves ingestion of 10 markers for 6 days at the same time and execution of a plain abdominal X-ray on the 7th day. During this week the patient will complete an evacuation diary recording the time and number of evacuations, the method of eventual bowel care, the consistency of faeces according to the Bristol Scale, any episode of fecal incontinence, the type of hygiene measures in general, the number of enemas, diapers, and any other garrison used in relation to the evacuation.

Patients will be asked to collect a faecal sample in a container during the last week before the following inspection at Visit 2.

During the second visit, the outcome of the plain abdominal X-ray will be discussed, the completed diaries will be collected, and the faecal sample will be stored at -20 C° and subsequently sent to the Laboratory of the Department of Pharmacy and Biotechnology of the University of Bologna, Italy for the analysis of the intestinal microbiome composition.

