Patients with severe NBD impairment will be offered the adoption of TAI as a way to manage their own evacuation, replacing any other measure used until that moment (suppositoires, enemas) with the exception of the possible intake of macrogols and/or prebiotics and/or probiotics which instead can be continued. This treatment will be proposed to all patients with severe impairment of intestinal function.

The TAI training with Peristeen will be carried out at the surgical clinic of the Surgical Department of the Ferrara University Hospital, Italy, by the personnel involved in the study, usually in a single session, but more sessions may be necessary.

During the following 4 weeks, patients will continue to use the Peristeen at home according to the instructions provided by the training staff collecting a stool sample each week. During the last of the four weeks of TAI use patients will repeat the compilation of food diaries, evacuation diaries, the radiopaque markers Transit Time, and collection of the stool for microbiota analysis. The appointment for the radiography could coincide also in this case with the following visit (visit 3 or 4).

During the last visit the outcome of Transit Time X-ray will be discussed, completed diaries and stool samples will be collected, and PAC-QoL questionnaire will be submitted to patients who completed the study pathway.

Patients will be asked about overall satisfaction of TAI treatment with Peristeen by means of a numerical assessment from 0 to 10.

Finally, any comment will be noted as well any events that might be related to TAI irrigation with Peristeen will be recorded.

Patients will undergo a neurological examination 3 months after the start of treatment.

The whole duration of the study will be of 2 years.

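### The before/after TAI comparisons are within-patient, but the analysis section names no paired test for ordinal, non-normal or binary data

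*Combined protocol and SAP*

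**What the plan says.** The Statistical analysis section lists its tests in one line: "Data will be analysed using Chi-square, t-student, and Mann-Whitney tests as appropriate". It does not say whether the t-test is paired, and it ties none of the three tests to an outcome. Summaries are chosen between median (IQR) and mean and "standard deviation according to distribution assessed by Shapiro-Wilk test", so the plan provides for non-normal data.

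Under Secondary Outcome Measures, outcome 3 is to "Compare the Scores of the assessment scales used before and after the 4-week TAI treatment period" and to "Calculate a possible advantage or non-benefit of the costs of treatment with TAI compared to the previous bowel management". Outcome 4 is to compare microbiota composition with a healthy regional profile and to "assess any changes after the period of treatment with TAI".

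The Study Protocol section shows that these are repeat measurements on the same people. In the last of the four weeks of TAI, "patients will repeat the compilation of food diaries, evacuation diaries, the radiopaque markers Transit Time", and stool is collected again. PAC-QoL is given again at the last visit to patients who finish the pathway. No other questionnaire is stated to be repeated. The evacuation diary records, among other things, "the consistency of faeces according to the Bristol Scale", which is an ordinal scale.

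**The concern.** No parallel control group for TAI is described, so the efficacy result rests on change within patients. Of the three named tests, only the t-test has a paired form. Mann-Whitney is the only rank test and Chi-square the only categorical test, and both assume independent observations. Choosing from the list therefore leaves no paired test for three kinds of before/after data: ordinal scores, continuous measures with non-normal differences, and binary measures such as slowed transit (yes/no) if classified at both times.

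Treating the two occasions as separate groups discards the pairing. The test then uses a standard error that is too large whenever a patient's two values are positively correlated, and a real change after TAI can be missed.

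Pairs will be few. Only the first 50 patients with PAC-QoL of at least 32 are invited to the second phase (Group Cohort; Study population), continuing depends on the patient's willingness (Study Protocol), and patients can be excluded during TAI training (Intervention).

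**Working it through.** The plan states no power, effect size or SD, so there is no figure of its own to reproduce. The check asks how much is lost if an independent-groups test is used on paired data.

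**From the documents:** significance at p < 0.05 (sidedness not stated); as written, at most 50 patients invited.

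**Assumed:** two-sided testing; within-patient correlation ρ of 0, 0.3, 0.5 or 0.7; 20, 30 or 50 pairs (25 or 50 in step 1); shifts of 0.3 to 0.8 SD; the distributions below.

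**Step 1: normal-theory check, change of 0.4 SD.** With unit SD and n pairs, the mean difference has true standard error √(2(1−ρ)/n), but an unpaired test uses √(2/n). Hence:

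- Actual type I error of the unpaired test = 2[1 − Φ(1.96/√(1−ρ))]: 5% at ρ = 0, 1.9% at 0.3, 0.6% at 0.5, 0.03% at 0.7.
- Paired power = Φ(0.4/√(2(1−ρ)/n) − 1.96). For n = 50, ρ = 0.5: Φ(2.83 − 1.96) = 81%.
- Unpaired power = Φ((0.4/√(2/n) − 1.96)/√(1−ρ)). For n = 50, ρ = 0.5: Φ((2.00 − 1.96)/0.707) = 52%.
- With 25 pairs at ρ = 0.5 the same formulas give 52% paired and 22% unpaired.

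Simulated rank tests on normal data agree: with 50 pairs at ρ = 0.5, Mann-Whitney has 48% power and signed-rank 77%.

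**Step 2: simulation for skewed and ordinal data.** Latent values are bivariate normal with SD 1 and correlation ρ, the second shifted by the stated amount. They are exponentiated (lognormal) or cut into 5 or 7 categories, with 10,000 replicates per cell. Entries are power (%) for Mann-Whitney / signed-rank, with the difference in points.

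| Data | Pairs | Shift (SD) | ρ = 0 | ρ = 0.3 | ρ = 0.5 | ρ = 0.7 |
|---|---|---|---|---|---|---|
| Lognormal | 30 | 0.5 | 45.5/40.5 (−5.0) | 44.5/52.9 (+8.4) | 44.9/67.1 (+22.2) | 44.0/85.4 (+41.4) |
| Lognormal | 30 | 0.3 | 20.1/18.2 (−1.9) | 16.7/23.3 (+6.6) | 12.7/29.9 (+17.2) | 8.1/45.5 (+37.4) |
| Lognormal | 20 | 0.5 | 31.8/28.2 (−3.6) | 29.3/37.3 (+8.0) | 27.2/47.9 (+20.7) | 23.9/68.0 (+44.1) |
| Lognormal | 50 | 0.5 | 66.5/60.6 (−5.9) | 70.2/75.3 (+5.1) | 72.8/86.9 (+14.1) | 78.8/97.6 (+18.8) |
| Ordinal, 5 categories | 30 | 0.5 | 43.0/41.9 (−1.1) | 42.7/54.8 (+12.1) | 41.8/67.6 (+25.8) | 40.7/84.6 (+43.9) |
| Ordinal, 7 categories | 30 | 0.5 | 44.1/42.0 (−2.1) | 44.0/54.6 (+10.6) | 42.4/66.9 (+24.5) | 41.1/85.4 (+44.3) |

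Reading down the columns, signed-rank loses 1 to 6 points at ρ = 0, gains 5 to 12 at 0.3, 14 to 26 at 0.5, and 19 to 44 at 0.7.

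**Step 3: type I error, no change (lognormal, 30 pairs).** Mann-Whitney rejects in 5.4%, 2.3%, 0.7% and 0.1% of samples at ρ = 0, 0.3, 0.5 and 0.7. Signed-rank stays between 5.0% and 5.5%.

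**Step 4: large effects (lognormal, shift 0.8 SD).** With 30 pairs, Mann-Whitney against signed-rank is 88% vs 90% at ρ = 0.3, 92% vs 97% at 0.5, and 95% vs 99.8% at 0.7. With 50 pairs at ρ = 0.3 both reach 99%.

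**Step 5: would a rank test be reached at all?** In the lognormal setting with 30 pairs and a shift of 0.5 SD, Shapiro-Wilk applied to the within-patient differences flags non-normality in 78% to 91% of samples (3,000 replicates per ρ). A paired t-test would then not be the default choice in most samples.

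**The case against.** The strongest reply is that this is a short, non-exhaustive list. It ends with a qualifier leaving the choice to the analyst, and it is not closed: outcome 1 is "To calculate the Correlation Coefficient between Intestinal Transit Time and the Bristol Score" and others, yet no correlation method appears in the analysis section. The t-test can be read as including its paired form, and Mann-Whitney and Chi-square have proper uses between different patients. This much stands. A reader might infer that the plan assigns Mann-Whitney to the before/after data; it does not. The qualifier cannot, however, turn Mann-Whitney or ordinary Chi-square into a paired test, and no signed-rank, McNemar or repeated-measures method appears anywhere in the documents.

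A reader might also infer a risk of false claims of efficacy, or a threat to the main results. Neither follows. With positive correlation the error is conservative, and the primary outcomes are not before/after comparisons.

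Three limits on the illustration also stand:

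- Effect, correlation and number of pairs are all assumed. At zero correlation the paired rank test is slightly worse, and for large effects the choice hardly matters. Selecting patients on PAC-QoL at entry may lower the correlation for that score, so the low-correlation columns may be the relevant ones for it.
- The Bristol Scale is recorded in a diary kept over a week, possibly for many stools per patient, and no patient-level summary is defined. One ordinal value per patient per occasion is a simplification.
- Outcome 4 is only partly served by a two-time-point test, because stool is collected weekly during TAI and microbiota composition is multivariate.

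**Conclusion.** The point holds as an omission with a concrete remedy. For ordinal, non-normal or binary before/after TAI data, keeping to the named tests means using an independent-groups test on paired observations. The likely cost is lost power on secondary outcome 3 and on the before/after part of outcome 4.

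Under the assumed inputs (20 to 50 pairs, shift 0.3 to 0.5 SD), the cost is modest at a correlation of 0.3 (about 5 to 12 points) and substantial at 0.5 (about 14 to 26). At zero correlation the sign reverses, with signed-rank 1 to 6 points behind. These figures are not estimates for this study, because the documents supply none of the inputs. The direction of the error for positive correlation does not depend on the particular values chosen.

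This is a cheap improvement to secondary analyses.

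**What to change.** Add to the Statistical analysis section:

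> Before/after TAI comparisons in the same patients (PAC-QoL, transit time, patient-level evacuation-diary summaries, costs and any other repeated univariate measure) will use the paired t-test or, when the within-patient differences are non-normal or the scale is ordinal, the Wilcoxon signed-rank test. Binary before/after measures (e.g. slowed transit yes/no) will use McNemar's test. The number of pairs will be reported for each comparison.

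Keep Mann-Whitney and Chi-square for comparisons between different patients. Two related items need their own wording. The weekly microbiota samples need a within-patient (repeated-measures) analysis, which the sentence above does not supply. The plan should also say how patients without a post-TAI value are handled, since PAC-QoL is repeated only in those who complete the pathway.

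The cost of the main change is a sentence or two of wording. It needs no extra data or visits, and the tests are routine. The one statistical downside is a small loss of power if the within-patient correlation is near zero.
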